1
2
3
4
5
6
7
8
9
10
11
12
13
14
15
16
17
18
19
20
21
22
23
24
25
26
27
28
29
30
31
32
33
34
35
36
37
38
39
40
41
42
43
44
45
46
47
48
49
50
51
Brooke Army Medical Center
Institutional Review Board

**HUMAN SUBJECTS RESEARCH
PROTOCOL APPLICATION – Part B**

1. PROTOCOL TITLE: Heated Ultrasound Gel Satisfaction (HUGS): A Randomized Control Trial

2. ABSTRACT: Ultrasound has become one of the fastest growing diagnostic tools for Emergency Physicians, and given the increasing focus on patient satisfaction in the Emergency Department, there may be opportunities to enhance both patient satisfaction and diagnostic accuracy. The purpose of this single-blind, randomized control trial will be to investigate whether simply having warm gel, as compared to room-temperature gel, during a bedside ultrasound significantly improves patient satisfaction scores. If satisfaction scores are significantly higher, then medical directors may find it beneficial to invest in ultrasound gel warmers. We will also investigate two secondary hypotheses: 1) patient perceptions of their medical providers and 2) the overall quality of ultrasound images obtained.

3. OBJECTIVES/SPECIFIC AIMS/RESEARCH QUESTIONS.
Hypothesis: The utilization of warmed ultrasound gel significantly increases patient satisfaction with regards to their care during a visit to the Emergency Department.
Null: The utilization of warmed ultrasound gel does not change patient satisfaction with regards to their care during a visit to the Emergency Department.

Hypothesis 2: Utilization of warmed ultrasound gel significantly improves the quality of images obtained during bedside ultrasound.
Null: The utilization of warmed ultrasound gel does not change the quality of images obtained during bedside ultrasound.

Hypothesis 3: The utilization of warmed ultrasound gel significantly increases patient perceptions of their physician's professionalism.
Null: The utilization of warmed ultrasound gel does not change patient perceptions of physician professionalism.

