62 patient in the long run. For example, one abdominal CT delivers 8mSv, which is roughly equivalent to the
63 radiation from 400 chest x-rays.⁴ To counter this increase in CT scans, ultrasounds have become one of the
64 fastest growing and safer diagnostic tools for ED physicians over the past decade. Non-cardiac ultrasound
65 use increased by 121% from 2002-2012, with 21 patients per 1000 being scanned.³ With real-time
66 diagnostic capabilities at the bedside and no harmful radiation, ultrasounds provide clinicians with decision
67 tools to better care for their patients. Class I medical devices, such as the Thermasonic® Gel Warmer, heat
68 ultrasound gel to- and just-above normal body temperatures are frequently seen in Cardiology and OB-GYN
69 clinics, where echocardiograms and pelvic ultrasounds are performed routinely. Given the increase in use of
70 ultrasound and the increased focus on patient satisfaction, our aim is to identify whether warmed gel can
71 truly improve overall patient satisfaction when performing point-of-care ultrasounds in the ED.

72 **6. RESEARCH DESIGN**

73 This is a single-blinded, randomized study will recruit a sample of 124 subjects from military and civilian
74 populations who are treated in the Emergency Department (ED) at SAMMC and require standard of care
75 bedside ultrasound for diagnosis.

76 **7. RESEARCH PLAN**

77 **7.1 Selection of Subjects**

82 **7.1.1. Subject Population.**

84 **7.1.2 Inclusion Criteria:**

- 85 • Adults 18-89 who are seen in the SAMMC Emergency Department that require standard of care
86 bedside ultrasound

88 **7.1.3 Exclusion criteria:**

- 89 • Minors under age 18
- 90 • Pregnant females
- 91 • Adults over age 90
- 92 • Vulnerable adults to include those with altered mental status, incarcerated, military basic trainees, or
93 those with a primary language other than English
- 94 • Patients with open or broken skin

96

7.1.2. Source of Research Material.

Source of Research Material	Clinical Purposes(Y/N)	Research Purposes (Y/N)
Patient Survey	N	Y
Provider Survey	N	Y
Bedside Ultrasound	Y (standard of care)	Y

97

98

99 **7.1.3. Description of the Recruitment and Prescreening Process.** Patients being treated in the ED who
100 require a standard of care bedside ultrasound for diagnosis will be approached by the AI (ultrasonographer).
101 The AI will advise patient that they are there to perform the ultrasound as ordered by his or her doctor and

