136 **7.3. Study Procedures/Research Interventions.** The principal investigator will brief ED physicians on details

137 of this study by email (Appendix D). ED physicians who identify that a patient will require an ultrasound will
138 page the ultrasound team as part of standard of care. At that time, the AI (ultrasonographer) will ask subject if
139 he/she would like to participate in a research study involving patient satisfaction and diagnostic bedside
140 ultrasound. If the patient agrees, the AI will provide an information sheet (Appendix C) and explain study
141 details/answer any questions. The patient will then be randomized and assigned a HUGS-X number that will be
142 placed in the comments section of the ultrasound image and given a 3-question patient survey (Appendix A)
143 related to patient satisfaction and perceptions about their provider which will be completed at the end of the
144 ultrasound procedure. The patient will be instructed not to provide any PII/PHI when he/she completes the
145 survey after the diagnostic bedside ultrasound and to hand it back to the AI when complete.

146
147 **Ultrasound and Warm or Room Temp Gel Procedures:**
148

149 The AIs will use either the warm or cold gel to complete their standard of care diagnostic ultrasound scans.
150 Subjects will be randomized to receive either warm or cold gel depending on the study packet number. The
151 study packet number will contain specific randomized instructions for the AI that provides the appropriate gel
152 numbered 1-6 to utilize and the 3-question patient survey and 1 question provider survey.

153 Patients and providers will be blinded to the intervention meaning both the AI and the patient will be
154 unaware of different gel temperatures being utilized until the moment it is used on the patient's ultrasound
155 area.

156 The provider (AI) will be blinded to the intervention used in two ways. The first being that six ultrasound gel
157 warmers, labeled #1-6, will be set up at a station, and the warmers will have been randomly set-up as far
158 which are actually turned on or not by the PI. The AI will not know which are turned on because the indicator
159 lights will be covered with black tape. Additionally, the AI will use heat-resistant gloves to hold the
160 ultrasound gel bottle as described in section 7.2.2. At the end of the subject's bedside ultrasound, the

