161 physician completing the ultrasound will hand the patient a satisfaction survey utilizing visual analog scales.
162 As an additional measure to test our blinding measure, the AI will complete the one question survey to test
163 whether he or she was aware of the warm or room-temperature gel temperature.

164 Both surveys will be collected and stored in a locked box in C-Pod of the Emergency Department until
165 results can be entered in to the electronic spreadsheet (HUGS DataTracker Data Collection Spreadsheet,
166 Appendix G)

167
168 **The Ultrasound Image Rating:**
169

170 Ultrasound image rating is conducted weekly by the SAMMC ED/Ultrasound Quality Assurance Team on a
171 weekly basis. These meetings are already a standard practice in our department to review every ultrasound
172 obtained in the department as a way to obtain feedback from all clinicians about the quality of their
173 ultrasound studies. Their standard metric for evaluation is a 5-point Likert-type scale. During this QA review,
174 scores related to images that have a HUGS ID in the comments area will be written down and provided to
175 the PI. Their standard metric for evaluation is a 5-point Likert-type scale.

176 Table I: Summary of Study Activity/Interventions
177

Assessment:	During ED Visit:	Weekly Ultrasound QA Session:
Screening	X	
Randomization	X	
Bedside Ultrasound	X	
Anonymous Patient Survey Appendix A)	X	
Provider Survey (Appendix B)	X	
Review of Ultrasound Images for Overall Quality		X

178
179 **7.3.1 Collection of Human Biological Specimens.** N/A
180

181 **7.3.1.1 Laboratory evaluations and special precautions.** N/A
182

183 **7.3.1.2 Specimen storage.** N/A
184

185 **7.3.2 Data Collection.** Subject specific data (patient age, gender, and their satisfaction scores) will all be
186 written on the anonymous survey (Appendix A). The primary outcome will be a visual analogue scale, i.e.
187 continuous variable. By collecting a variable with greater data density than a conventional Likert scale (e.g.,
188 ordinal data), this will enable us to use more powerful statistical techniques in analyzing our data so minimizing
189 the possibility of a type II (beta) error. We will further evaluate our secondary outcomes with Likert-type scales
190 to minimize millimeter differences between patient scores. Finally, we will use binary data to evaluate whether
191 patients were overall satisfied with their visit.
192

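### Section 7.3.2 rules out bias by calling every investigator blinded, yet the PI sets the warmers and may log the data, and reusable gel numbers can give operators foreknowledge of the arm

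*Combined protocol and SAP*

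**What the plan says.** Section 7.3 has six warmers, "labeled #1-6, will be set up at a station, and the warmers will have been randomly set-up as far" as which are switched on; the PI does this. The packet directs the AI to a gel "numbered 1-6 to utilize and the 3-question patient survey and 1 question provider survey". Indicator lights are taped over, and the AI holds the bottle in heat-resistant gloves.

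The same section defines the blinding and its end point: "Patients and providers will be blinded to the intervention meaning both the AI and the patient will be" "unaware of different gel temperatures being utilized until the moment it is used on the" patient. It also provides a check: "As an additional measure to test our blinding measure, the AI will complete the one question survey to test" awareness of the temperature.

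For image quality, "scores related to images that have a HUGS ID in the comments area will be written down and provided to" the PI. Section 7.3.2 lets the PI or an available AI collect completed packets, log the survey data and log the image scores. It then concludes that bias in rating or data entry is not a concern, and the only reason given is that the investigators, without exception, do not know which scans used warm gel.

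On the label, the Abstract states: "The purpose of this single-blind, randomized control trial will be to investigate" the effect of warm gel. Section 6 agrees: "This is a single-blinded, randomized study will recruit a sample of 124 subjects from military and civilian" populations.

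**The concern.** Three things do not fit together.

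- **The blanket blinding claim.** The PI holds the on/off pattern and may also handle outcome data. The AIs are investigators too, and section 7.3 ends their blinding at application. Section 7.3.2 therefore rests its dismissal of bias on a premise that other parts of the plan contradict.
- **The gel number as a reusable arm code.** If the pattern stays the same, what an AI learns about one warmer in one scan carries over to the next subject given that number. Tape and gloves hide the current bottle; they do nothing about memory. The AI performs the scan, hands over the survey and takes it back. Satisfaction with the ultrasound (1a) and perceived professionalism are subjective ratings of that encounter, so an AI who knows the arm beforehand could, even unconsciously, change manner or preparation.
- **The label.** Single-blind in the Abstract and section 6 conflicts with blinding of both patient and provider in section 7.3.

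**Working it through.** **1. The blanket claim, by role**

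| Role | What the plan gives them | Blinded throughout? |
|---|---|---|
| PI | Sets the warmers (7.3); receives image scores (7.3); may collect packets and log surveys and scores (7.3.2) | No: knows the pattern. Identifying the arm of one record also needs the packet-to-gel-number link; no barrier to that link is described |
| Scanning AI | Uses a numbered gel from a warmer of masked status | Only until the gel is used (7.3) |
| Image raters | See the HUGS identifier in the comments box (7.3, 7.5) | No passage shows that they learn the arm |

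One role with the pattern in hand is enough to make the universal statement untrue.

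**2. Reuse of gel numbers**

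From the documents: 114 + 10 = 124 subjects (7.4.1), six numbers (7.3), 12 months of recruitment (13.0), taken as 52 weeks.

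- Uses per number, if equal: 124/6 = 20.7.
- Subjects per week: 124/52 = 2.4.

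Assumed, because the documents do not say: *k* operators sharing the scans at random, numbers equally likely, the pattern unchanged, each use recognised with probability *r*, and a stated length of recall.

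Call a scan exposed if the same operator has already recognised that number. With *r* = 1 and perfect recall there are *c* = 6*k* operator–number pairs, and every scan after the first in a pair is exposed:

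share = 1 − *c*[1 − (1 − 1/*c*)^124]/124

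For *k* = 5, *c* = 30: (29/30)^124 = 0.015; 30 × 0.985 = 29.55; 29.55/124 = 0.238; share = 76.2%. If all operators pooled what they knew (*k* = 1), 118 of 124 scans (95%) would be exposed.

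The first row below follows from this formula; the others come from simulation on the same assumptions.

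| Illustrative assumptions | 3 operators | 5 | 8 | 20 |
|---|---|---|---|---|
| Fixed pattern, *r* = 1, perfect recall | 85.5% | 76.2% | 64.1% | 37.5% |
| Fixed, *r* = 1, 12-week recall | 72.8% | 55.2% | 40.0% | 18.7% |
| Fixed, *r* = 1, four-week recall | 39.5% | 26.3% | 17.3% | 7.3% |
| Fixed, *r* = 0.25, four-week recall | 11.8% | 7.2% | 4.6% | 1.9% |
| Weekly re-draw, balanced warm/room-temperature list, *r* = 1 | about 7.5% | about 4.7% | about 2.9% | about 1% |

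These are shares of scans in which foreknowledge would be possible. They are not estimates of bias, and the range from about 2% to 85% shows how far they depend on undocumented inputs.

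**The case against.** The strongest reply is that the foreknowledge argument rests on silence. Section 7.3 does not say that the set-up happens only once, and the packet instructions and appendices are not in the text available. That stands: this is a gap in the plan, not proof that the pattern never changed.

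The harm is also narrow. An AI who recognises the temperature during a scan is unblinded for the rest of that scan under any coding, so the numbering adds only knowledge before application. Nor does the stated end point of blinding show that AIs actually identify the temperature; they handle the bottle with a sterile glove over a terry-cloth glove (7.2.2). Both points stand.

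On the PI, knowing the pattern unblinds a record only if that record can be tied to a gel number. Images carry the HUGS number, and no passage says that surveys or image comments carry the gel number. A reader might infer that the PI is shown to know the arm of every record, or that the image raters are unblinded. The documents support neither. What they do show is that the PI is not blinded to the pattern and that no separation is described.

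The provider survey helps, and section 7.3.2 already foresees evaluating the answers. But as described it asks about awareness of the temperature, so it cannot separate prior knowledge from recognition during the scan, and it prevents neither. Section 7.4.3 gives no analysis of it.

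**Conclusion.** The statement in section 7.3.2 is wrong as written for the PI, and wrong for the AIs once gel is applied, so it cannot carry the conclusion that bias is of no concern. The conflict over the single-blind label is likewise plain on the text. Neither conclusion depends on any assumed number.

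The reusable gel number is a real route to foreknowledge under the single set-up described, with about 21 uses per number if use is equal. How often it would operate depends on operator count, recognition and recall, none of which is documented. A reader might go further and infer from the high exposure figures that outcome 1a is biased by some amount. Nothing in the documents supports a size or a direction, and none is claimed here. The point deserves correction because the remedy is cheap, not because harm has been demonstrated. Sample size and outcomes are unaffected.

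**What to change.** 1. **Separate the key from the data.** The PI, as holder of the warmer key, does not log survey data or image scores. An AI who did not perform that scan logs them; section 7.3.2 already allows an AI to do so. Keep the gel number off the surveys and image comments. Cost: data entry moves from the PI to an AI.
2. **Re-draw the warmers.** The PI re-draws the on/off pattern at set intervals, with at least one on and one off, and keeps a dated key. Packets are issued for each interval so that the packet number still fixes the arm, and each gel number is checked against the current key at issue. Cost: a recurring set-up task, time for warmers to heat or cool, and a small risk of wrong-arm packets that the check must control. A longer interval is less work but protects less. If the set-up is already meant to be repeated, say so and give the interval.
3. **Correct the text.** Replace the blanket statement in section 7.3.2 with who is blinded to what and until when, and reconcile it with the single-blind label in the Abstract and section 6. Report provider-survey answers by arm, and state unblinding after gel application as a limitation, since no re-draw removes it. Cost: a paragraph and one table.

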4. MILITARY RELEVANCE. Patient satisfaction as an indicator of the quality of healthcare has evolved as an outcome measure within both the federal and civilian sectors. In fact, the DOD military health system incorporated patient satisfaction surveys to serve as a measure for how its beneficiaries perceive their care.⁶ In order to further review specific factors that may help to improve patient satisfaction scores, this study will explore the use of warmed ultrasound gel and perceived patient satisfaction. For most soldiers and dependents, warmed ultrasound gel is generally more comfortable than room temperature gel because warmed gel appears to enhance patient comfort and improve overall experience with the procedure. There is a considerable gap in the literature regarding factors that improve enhanced patient comfort in military beneficiary populations. Therefore, one of the contributions of this study will be to clarify precisely what that level of satisfaction is, if use of warmed gel is truly a satisfaction factor, and if the quality of images improve with the use of warmed gel. Generally, we aim to contribute to the generalizable knowledge of medical science, particularly in regards to patient satisfaction and the impact of warmed gel on ultrasound imaging, which would be applicable to both military and civilian settings.

5. BACKGROUND AND SIGNIFICANCE. Patient satisfaction is a growing center focus of Emergency Departments across the country. One study evaluated over 2.4 million ED visits over the course of four

52 years in eight different states. Their data showed that patients who responded with the lowest quarter of
53 satisfaction scores were twice as likely to file a complaint compared to the top quarter of patients surveyed.¹
54 In a 2005 study in *JAMA*, 93% of physicians in Pennsylvania from six of the most litigious medical services
55 reported that they practice “defensive medicine and within this group, ED physicians had the highest rates of
56 ordering more tests than medically necessary.²

57
58 In line with the concept of more tests than medically necessary, CT orders in the ED are becoming standard
59 of practice as a method of evaluating a wide variety of complaints. Levin, Parker, and Fragos (2014)
60 reported that for every 1000 Medicare ED visits between 2002-2012, CT scanner use increased remarkably
61 across the country.³ The doses of radiation that come with CT scans, however, can increase the risk to the

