193 Primary Outcome #1a: Overall, how satisfied are you with the experience of having a bedside ultrasound today?
194• Ranges from “Least” to “Most” on 10cm VAS (continuous data)
195

196 Primary Outcome #1b: Overall, are you satisfied with the care you received today in the Emergency
197 Department?
198• “Yes” or “No” (binary data)
199

200 Secondary Outcome #1: Overall, how professional was the physician who did your bedside ultrasound?
201• Ranges from “Least” (1) to “Most” (5) on 5-point Likert-type scale (ordinal data)
202

203 The subject survey form will not contain any PHI/PII. Completed packets will be taken to the locked bin in C-Pod
204 of the Emergency Department. We will also store the completed provider surveys in the same container to allow
205 for further evaluation of provider answers regarding which type of gel they believe they used and if the blinding
206 method imposed by the PI prevented the provider from knowing which gel they utilized.
207

208 New study packets will be kept in a separate designated bin within the Emergency Department, next to the
209 ultrasound gel warmers, so that associate investigators may access all required materials while working in the
210 department. The PI or available AI will pick up completed packets weekly and will either log the data
211 immediately or store them in the designated locked bin in the ultrasound team room until they can be entered
212 into the HUGS DataTracker spreadsheet.
213

214 Subject bedside ultrasounds, like any clinical ultrasound done in our hospital, are uploaded automatically to the
215 IMPAX system. Each week, the SAMMC ED/Ultrasound Quality Assurance Team reviews all bedside
216 ultrasounds for quality assurance purposes. Their standard metric for evaluation is a 5-point Likert-type scale.
217 This type of data is ordinal (and is the basis for secondary outcome #2). These scores will be logged by the PI or
218 available AI into an Excel Spreadsheet found on a password-protected computer behind a locked door in the
219 ultrasound team room. As all investigators are blinded to which ultrasounds were conducted with warm or cold
220 gel, there is no concern for a bias regarding the rating of quality for each ultrasound or during entering survey
221 data to the HUGS DataTracker. Upon transfer of all data to the spreadsheet, the paper surveys and hand-
222 written scores for each ultrasound will be shredded.
223

224 **7.4 Statistical Consideration**

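### Hypothesis 1 is about satisfaction with ED care, but the only powered outcome (#1a) measures satisfaction with the bedside ultrasound, and the role of the second item labelled primary (#1b) is not stated

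*Combined protocol and SAP*

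**What the plan says.** **Hypothesis (section 3).** Hypothesis 1 reads "The utilization of warmed ultrasound gel significantly increases patient satisfaction with regards to their care during a visit to the Emergency Department". Its null reads "The utilization of warmed ultrasound gel does not change patient satisfaction with regards to their care during a visit to the Emergency Department". Both concern care during the ED visit.

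**Outcomes (section 7.3.2).** The opening paragraph speaks of one primary outcome: "The primary outcome will be a visual analogue scale, i.e"., a continuous variable. After the secondary outcomes it adds the binary item: "Finally, we will use binary data to evaluate whether" patients were satisfied overall with their visit. The list that follows labels two items primary. #1a is a 10 cm VAS on the experience of having the bedside ultrasound. The other is "Primary Outcome #1b: Overall, are you satisfied with the care you received today in the Emergency" Department, answered Yes or No.

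**Endpoints and sample size (sections 7.4.1 and 7.4.2).** The required size of 114 is built on an 11 mm difference and a 21 mm SD on the VAS. Section 7.4.2 says the study is powered for the primary outcome and identifies it as 1a. It then lists #1a, #1b, #2 and #3, and gives #1b neither a primary nor a secondary label.

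**Analysis (section 7.4.3).** Satisfaction scores are compared by t-test, or by the non-parametric equivalent if the data are ordinal or not normal with equal variances. No method is named that clearly covers Yes/No data.

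**Rationale (sections 2, 4 and 5).** The abstract asks whether warm gel "during a bedside ultrasound significantly improves patient satisfaction scores". Section 4 says "warmed gel appears to enhance patient comfort and improve overall experience with the procedure". Section 5 gives the aim as learning whether warmed gel can "truly improve overall patient satisfaction when performing point-of-care ultrasounds in the ED".

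**The concern.** The formal hypothesis and the powered test do not ask the same question. An ultrasound is part of ED care, but only part of it, and the survey asks about the whole in a separate item. A patient could be pleased with the scan and displeased with the visit, or the reverse. If #1a is significant, what has been rejected is a null about the ultrasound experience, not the null in section 3.

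Two misreadings are then open. A positive #1a could be reported as better satisfaction with ED care, which is more than it measures. Or #1b, the item that matches the hypothesis wording, could be brought forward: presented as a second primary result if positive, or read as evidence of no effect if null, when the trial has little power for it. The abstract says a positive satisfaction result may lead medical directors to buy gel warmers, so the breadth of the claim matters in practice.

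**Working it through.** **1. Which outcome was the trial sized on?**

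Inputs from section 7.4.1: difference 11 mm, SD 21 mm, two-sided alpha 0.05, power 0.80, equal arms.

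n per arm = 2 × (1.960 + 0.842)² × (21/11)² = 2 × 7.849 × 3.645 = 57.2, or 114.4 in total.

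This reproduces the stated 114 (57 per arm); rounding up gives 58 per arm, 116 in total. Adding 10 for drop-out gives the stated 124. The noncentral-t power at 57 per arm with d = 11/21 is 79.2%. The sample size therefore follows from #1a alone.

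**2. What does that sample size offer #1b?**

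The documents give no Yes rates, so the three pairs below are assumptions. Power is by exact enumeration of two independent binomials, two-sided 0.05.

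| Assumed Yes rates | Fisher, 57/arm | Chi-square (uncorrected), 57/arm | Fisher, 62/arm | Chi-square (uncorrected), 62/arm |
|---|---|---|---|---|
| 80% vs 90% | 23% | 32% | 26% | 34% |
| 85% vs 95% | 30% | 44% | 34% | 47% |
| 90% vs 95% | 8% | 17% | 9% | 18% |

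The 62-per-arm columns take all 124 enrolled as evaluable.

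Expected 95% CI half-width for the risk difference at 57 per arm, 1.96 × √{[p₁(1−p₁) + p₂(1−p₂)]/57}:

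- 80 vs 90%: 1.96 × √(0.2500/57) = 13.0 points
- 85 vs 95%: 1.96 × √(0.1750/57) = 10.9 points
- 90 vs 95%: 1.96 × √(0.1375/57) = 9.6 points

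The assumed differences are 10, 10 and 5 points, so in each case the half-width exceeds the difference.

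**3. What would an ED-care primary outcome need?**

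If it stays Yes/No, with p̄ the mean of the two rates:

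n per arm = [1.960√(2p̄(1−p̄)) + 0.842√(p₁(1−p₁) + p₂(1−p₂))]² / (p₁−p₂)²

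- 80 vs 90%: 198.96, so 199
- 85 vs 95%: 140.1, so 141
- 90 vs 95%: 434.4, so 435

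The smallest sizes giving at least 80% power by Fisher's exact test are 214, 151 and 466 per arm.

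If ED care were instead measured on a VAS, and 11 mm with SD 21 mm were assumed to hold there too, step 1 applies unchanged: about 57 to 58 per arm.

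**4. Error rate, as illustration only.**

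If success on either item counted at 0.05 each, the family-wise error would be 1 − 0.95² = 9.75% under independence and at most 0.05 + 0.05 = 10% in general. No section states such a rule. If #1a alone governs, there is no inflation.

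**The case against.** **The plan already settles that #1a is primary.** Largely true: 7.3.2 describes one VAS primary outcome and 7.4.2 names only 1a. That removes most of the multiplicity worry. It assigns no inferential role to #1b, and it makes the mismatch with Hypothesis 1 plainer.

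**The numbering shows that #1a and #1b together address Hypothesis 1.** This is probably the intent, since #2 and #3 line up with Hypotheses 2 and 3. On that view ED care is measured. But no rule says how the two items combine, and the one that matches the hypothesis wording is the unpowered one.

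**The hypothesis may be right and the outcome wrong.** This stands in part. The abstract, section 4 and the stated aim in section 5 tie satisfaction to the procedure, but the abstract and section 5 also open from satisfaction in the ED generally. The rationale is mixed, so rewording the hypothesis is the cheaper repair, not the only one the text allows.

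**An ED-care hypothesis need not mean a much larger trial.** Also right. The 141 to 466 per arm apply only if the outcome stays Yes/No. Whether warmed gel could move an ED-care VAS by 11 mm is unknown.

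**A stronger reading to avoid.** A reader might infer that the trial has two primary outcomes and an inflated type I error. The documents do not support that: no section lets either item win, and 7.3.2 and 7.4.2 point to #1a alone.

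**Conclusion.** The point holds and should be fixed. As worded, Hypothesis 1 is broader than the only powered outcome, so a significant #1a would not by itself support it. #1b carries a primary label that sits badly with the rest of 7.3.2 and with 7.4.2, and its part in the inference is nowhere stated.

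In size: 79% power for #1a at 57 per arm, against about 8 to 30% (Fisher) or 17 to 44% (uncorrected chi-square) for #1b. The #1a figure rests on the protocol's own inputs. Every #1b figure rests on assumed Yes rates, though the conclusion that #1b is unpowered is the same in all three scenarios and with all 124 evaluable.

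This does not invalidate the trial or its sample size for #1a. What is at stake is which claim the result can carry. The mismatch and the label conflict are read directly from the text; the choice of remedy is a matter of judgement.

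**What to change.** **Preferred changes**

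- Sections 7.3.2 and 7.4.2: name #1a the sole primary outcome, tested at two-sided 0.05. Relabel #1b as secondary or supportive, and state that it cannot establish the primary claim alone.
- Section 3: reword Hypothesis 1 and its null to patient satisfaction with the bedside ultrasound experience.
- Section 7.4.3 (minor): compare #1b with a prespecified test for two proportions, and report the risk difference with a 95% CI.

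**Cost.** Wording only. The sample size stays at 114 + 10 = 124 and no new data are needed. The downside is a narrower primary claim.

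**Alternative.** If the investigators want to keep the ED-care hypothesis, the primary outcome must measure ED care and the trial must be sized on that outcome. If it stays Yes/No, this means about 141 to 466 per arm under the assumed rates. If it is a VAS, it means about 57 to 58 per arm, provided 11 mm and SD 21 mm can be justified for that question, and a new survey item.
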